8.5.4. Pure Class V Exploratory Endpoints

Exploratory endpoints in the pure Class V LN patients include:

- Proportion of patients that achieved CRR at Weeks 37 and 53
- Proportion of patients that achieved PRR at Weeks 37 and 53
- Change from Baseline in antibodies (anti-dsDNA antibody, C1q autoantibody)
- Change from Baseline in complement (C3, C4)
- Change from Baseline in 24-hour urine protein
- Change from Baseline in serum albumin

- Change from Baseline in serum creatinine
- Change from Baseline in eGFR
- Change from Baseline in serum lipids (LDL cholesterol, serum total cholesterol, serum triglycerides)
- Change from Baseline in IgM, IgG and IgA

These exploratory endpoints will be analyzed using similar methods as described in Section 8.5.1 and Section 8.5.3, as applicable.

8.5.5. Other Exploratory Endpoints

Other exploratory endpoints include:

- Pharmacogenomics profile (ribonucleic acid [RNA] sequencing) and biomarkers, such as serum cytokine levels and circulating leukocytes to be determined in blood samples and urinary biomarkers
- Pharmacokinetics profile

Analysis of these endpoints is outside the scope of this SAP. See Section 8.6.2, Section 8.6.3, and Section 10 for additional information regarding these endpoints.

8.6. Biomarker Assessments

8.6.1. Cytokine Activity

Blood samples for assessment of cytokine activity and circulating leukocytes will be collected prior to study treatment administration at the visits specified in the Schedule of Assessments (Appendix 1).

Cytokine activity and circulating leukocytes will be summarized by treatment group and visit for the Safety Population.

All cytokine activity and circulating leukocyte data will be listed for the Safety Population.

8.6.2. Gene Expression/Pharmacogenomics

Blood samples for assessment of gene expression (RNA) profiling and genomic DNA genotyping will be collected prior to study treatment administration at the visits specified in the Schedule of Assessments (Appendix 1). These analyses are outside the scope of this SAP.

8.6.3. Urine Biomarkers

24-hour urine and urinalysis samples will be collected at the visits specified in the Schedule of Assessments (Appendix 1). A portion of these samples will be utilized by the central laboratory to identify urine biomarkers for response and/or safety.

Analyses of these samples are not included in this study and are outside the scope of this SAP.

8.7. Glucocorticoid Toxicity Index

The following continuous GTI scores will be summarized by treatment group (mean, standard deviation, median, interquartile range, minimum, maximum) and post-baseline visit for the ITT Population:

• GTI-CWS

- Calculated as the sum of the maximum weighted scores for each of the 8 GTI domains from baseline through the visit of interest
- The GTI-CWS can only increase or stay the same for the duration of the study
- Lower GTI-CWS is associated with lower glucocorticoid toxicity over time

• GTI-AIS

- Calculated as the sum of the weighted scores for each of the 8 GTI domains at the visit of interest
- Lower GTI-AIS is associated with lower glucocorticoid toxicity over time

The 8 GTI domains will be listed for the ITT Population. Changes are with respect to the most recent previous on-study GTI assessment. Weighted scores for each category are noted in brackets below. More details can be found in the GTI Requirements Document (Appendix 5) and Weighting, Scoring and Analysis of the GTI (Appendix 6).

• Change in BMI

- Decrease of ≥5 BMI units [-36]
- Decrease of >2 to <5 BMI units [-21]
- No significant change (+/- 2 BMI units) [0]
- Increase of >2 to <5 BMI units [21]
- Increase of ≥5 BMI units [36]

• Glucose metabolism

- Improvement (decrease) in HbA1c AND decrease in use of glucose control medication [-44]
- Improvement (decrease) in HbA1c OR decrease in use of glucose control medication [-32]
- No significant change [0]
- Increase in HbA1c OR increase in use of glucose control medication [32]
- Increase in HbA1c AND increase in use of glucose control medication [44]

• Blood pressure (BP)

 Improvement (decrease) in BP AND decrease in use of BP control medication [-44]

- Improvement (decrease) in BP OR decrease in use of BP control medication [-19]
- No significant change [0]
- Increase in BP OR increase in use of BP control medication [19]
- Increase in BP AND increase in use of BP control medication [44]

• Hyperlipidemia

- Decrease in LDL AND decrease in use of lipid control medication [-30]
- Decrease in LDL OR decrease in use of lipid control medication [-10]
- No significant change [0]
- Increase in LDL OR increase in use of lipid control medication [10]
- Increase in LDL AND increase in use of lipid control medication [30]

• Steroid myopathy

- Moderate weakness to none [-63]
- Moderate to mild weakness [-54]
- Mild weakness to none [-9]
- No significant change [0]
- None to mild weakness (without functional limitation) [9]
- Mile to moderate weakness [54]
- None to moderate weakness (with functional limitation) [63]

Skin steroid-related toxicity

- Decrease in skin toxicity moderate to none [-26]
- Decrease in skin toxicity moderate to mild [-18]
- Decrease in skin toxicity mild to none [-8]
- No significant change [0]
- Increase in skin toxicity none to mild [8]
- Increase in skin toxicity mild to moderate [18]
- Increase in skin toxicity none to moderate [26]

• Neuropsychiatric (NP) steroid-related symptoms

- Decrease in NP toxicity moderate to none [-74]
- Decrease in NP toxicity moderate to mild [-63]
- Decrease in NP toxicity mild to none [-11]
- No significant change [0]
- Increase in NP toxicity none to mild [11]

Kezar Life Sciences, Inc. KZR-616-202

Statistical Analysis Plan, Version 1.0 Date Issued: 24Jul2024

- Increase in NP toxicity mild to moderate [63]
- Increase in NP toxicity none to moderate [74]

• Infection

- No infection [0]
- Oral/vaginal candidiasis or non-complicated zoster (< Grade 3) [19]
- Grade 3, 4, or 5 infection [93]

9. SAFETY ANALYSIS

All summaries of safety will be performed for the Safety Population using descriptive statistics, unless otherwise noted. All safety data will be listed for the Safety Population.

Safety assessments will include AEs, clinical laboratory tests, vital sign measurements, physical examinations, weight, 12-lead electrocardiogram (ECG), urine pregnancy testing, and hepatitis B DNA assessments (for HBcAb-positive patients only).

9.1. Adverse Events

AEs from signing IC form through 30 days after last dose of study treatment will be recorded on the "Adverse Events" eCRF. A TEAE is defined as an AE that emerges during treatment having been absent pre-treatment or an AE that worsens relative to the pre-treatment state (ICH-E9, 1998).

In general, TEAEs will be summarized using cumulative incidence rates of TEAEs and exposure-adjusted incidence rates (EAIR) within each treatment group, and pairwise differences between zetomipzomib and placebo with point estimates and 95% CIs. Cumulative incidence rate is defined as the number of patients who experienced the specific event divided by the number of patients included in the analysis. Patients with multiple occurrences of the same event will be counted only once in the numerator. See Section 9.1.12 for details regarding EAIR.

Missing/partial AE start dates will be imputed as specified in Section 4. AEs will be coded using MedDRA Version 26.1 or higher. In general, summaries will be provided by treatment group, SOC and PT, and will provide both total number of events and number (percentage) of patients experiencing at least one event. SOCs will be presented in descending order of frequency overall, and alphabetically in the event of ties. PTs within each SOC will be presented in descending order of frequency. At each level of summarization, patients will be counted once if they reported more than one event within the same PT.

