If a disease flare occurs during the study, patients may receive rescue therapy (see Section 6.2.3 for additional details). These patients will be discontinued from zetomipzomib or placebo but will be encouraged to remain in the study as outlined in the Schedule of Assessments (Appendix 3) through End of Study (EOS). Similarly, patients who do not receive rescue therapy but undergo a permanent discontinuation of zetomipzomib or placebo will also be encouraged to remain in the study through EOS. If the patient cannot continue with the planned assessments, the Early Termination Visit (ETV) and the 4-week safety follow-up (EOS) visit will be accomplished at a minimum.

Samples for sparse PK collection will be obtained for all patients at the following time points:

- 2 ( $\pm 15$  minutes) hours post dose at Week 25
- $0.5 (\pm 10 \text{ minutes})$  hours post dose at Week 37

Optional PK samples will be obtained in approximately 30 patients at selected centers at Week 5 at the following time points:

[figure not shown]
• pre dose and then at 0.5 ( $\pm 10$  minutes), 1 ( $\pm 10$  minutes), 2 ( $\pm 15$  minutes), and 4 ( $\pm 15$  minutes) hours post dose.

There will be an interim analysis (IA) when approximately 50% of the randomized patients with Class III/IV +/-V LN have completed or would have completed the Week 37 visit. This IA will serve the following purposes: (1) futility analysis and (2) a potential sample size increase up to 50% for patients with Class III/IV +/-V LN based on conditional power. An Independent Data Monitoring Committee (IDMC) will periodically review unblinded patient safety data and the IA results. A Steering Committee will be formed to receive the IDMC recommendations. Details of the IA will be outlined in the statistical analysis plan (SAP).

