## 9.1.5. Follow-up of Adverse Events

AEs are intended to be collected, according to the procedures outlined, from the time of informed consent and continuing for 30 days following the last dose of zetomipzomib or placebo or the EOS visit, whichever occurs later.

All Investigators should follow patient AEs until the event is resolved or until, in the opinion of the Investigator, the event is stabilized or determined to be chronic. Details of AE resolution must be documented in the eCRF.

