#### 9.2.2. Serious Adverse Event Reporting and Documentation Requirements

An SAE must be reported (see Section 9.1.6) by the Investigator if it occurs from the time of signed consent through 30 days after the last dose of zetomipzomib or placebo or the EOS visit, whichever occurs later, whether or not the SAE is considered to be related to treatment. After the

reporting period, SAEs should only be reported if the Investigator assesses the event to be related to study treatment.

Every SAE that occurs during the reporting period regardless of suspected causality must be reported by the Investigator in the electronic data capture (EDC) system (AE/SAE eCRF) within 24 hours from the time the Investigator becomes aware of the SAE. If there are any issues with EDC, a completed paper SAE report form should be emailed or faxed within 24 hours for the attention of the Project Manager (see Study Personnel page). Additional source documents can be requested, if deemed necessary.

The Investigator should not wait for additional information to fully document the event before notification of an SAE, though additional information may be requested. Where applicable, information from relevant laboratory results, hospital case records, and autopsy reports should be obtained. Follow-up information should be submitted in the same way as the original SAE report.

Instances of death, congenital abnormality, any SAEs, or an event of such clinical concern as to influence the overall assessment of safety, if brought to the attention of the Investigator at any time after cessation of zetomipzomib or placebo administration and considered by the Investigator to be related to participation in this study, should be reported to the Medical Monitor and to

The Sponsor and/or designee will promptly notify all relevant Investigators and the regulatory authorities of findings that could adversely affect the safety of patients, impact the conduct of the study, or alter the IDMC (or appropriate alternative)/Institutional Review Board (IRB)/Independent Ethics Committee (IEC) approval/favorable opinion of the study. In addition, the Sponsor or designee will expedite the reporting of all adverse reactions that are both serious and unexpected to all concerned Investigators, to the IDMC (or appropriate alternative)/IRBs/IECs where required, and to relevant regulatory authorities.

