ACR=American College of Rheumatology; AEs=adverse events; anti-dsDNA=anti-double stranded DNA; CBC=complete blood count; DNA=deoxyribonucleic acid; ECG=electrocardiogram; eCRF=electronic case report form; EOS=End of Study; EOT=End of Treatment; EQ-5D-5L=EuroQol 5-Dimension 5-Level; ETV=Early Termination Visit; EULAR=European Alliance of Associations for Rheumatology; GFR=glomerular filtration rate; GTI=Glucocorticoid Toxicity Index; HbA1c=hemoglobin A1c; HBcAb=hepatitis B core antigen antibody; HBsAb=hepatitis B virus surface antibody; HBsAg=hepatitis B virus surface antigen; HIV=human immunodeficiency virus; Ig=immunoglobulin; IgA=immunoglobulin A; IgG=immunoglobulin G; IgM=immunoglobulin M; MMF=mycophenolate mofetil; MPA=mycophenolic acid; NA=not applicable; PGA=physician global assessment of disease activity; QTc=QT interval corrected; SLE=systemic lupus erythematosus (includes lupus nephritis); SLEDAI-2K=Systemic Lupus Erythematosus Disease Activity Index 2000; TB=tuberculosis; WOCBP=women of child bearing potential.

- The end of study/safety follow-up visit will occur 4 weeks after the last dose of zetomipzomib or placebo.
- b HBsAg, HBcAb, hepatitis C antibody, and HIV; QuantiFERON®-TB Gold/Gold Plus or T-SPOT® TB test. Positive screens may require additional testing. At Screening, HBcAb-positive patients will have additional tests of HBsAb titer, and hepatitis B DNA to determine eligibility.
- c For those HBcAb-positive patients permitted to enter the study (HBcAb positive, HBsAg negative, HBsAb titer ≥100 IU/mL, and negative hepatitis B DNA), additional assessments for hepatitis B DNA should be performed at the indicated visits.
- d A chest x-ray will be obtained during the Screening period if not available from within 90 days prior to signing informed consent form.
- A full physical examination is conducted at Screening visit only. A symptom-directed brief physical examination will be completed at all other visits. Height will be measured at the Screening visit only, and body weight will be collected throughout the study. If visit is being conducted as a telehealth visit, weight will not be collected.
- f A 12-lead ECG with QTcF interval should be completed prior to vital signs, following 10 minutes of supine rest at indicated visits. The ECG at Week 25 should also be completed between 30 minutes to 4 hours postdose.

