- P Sparse PK samples will be drawn in all patients at Week 25 at 2 (±15 minutes) hours post dose and at Week 37 at 0.5 (±10 minutes) hours post dose. Optional PK samples will be drawn in a subset of ~30 patients at pre dose and 0.5 (±10) hours, 1 hour (±10 minutes), 2 hours (±15 minutes), and 4 hours (±15 minutes) post dose.
- q All AEs must be recorded on the patient's eCRF, starting at the time of informed consent and continuing through 4 weeks post-last dose.

Signature Page for		v1.0
--------------------	--	------

Approval Task	
	27-Jan-2023 00:17:19 GMT+0000
Approval Task	
	27-Jan-2023 04:45:35 GMT+0000
Approval Task	
	27-Jan-2023 04:58:31 GMT+0000
Approval Task	
	27-Jan-2023 14:51:46 GMT+0000

Signature Page for

v1.0

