Patients will be evaluated for eligibility according to the inclusion/exclusion criteria (see Sections 4.2 and 4.3 of the study protocol) within 5 weeks before the first dose of zetomipzomib or placebo on Day 1 (Week 1). Safety will be assessed throughout the study by monitoring vital signs, physical examinations, ECGs, and clinical laboratory tests and by recording and analyzing all treatment-emergent adverse events (TEAEs) and serious adverse events (SAEs). Blood samples for sparse and optional pharmacokinetic (PK) collection will also be drawn. Time points for all efficacy, safety, and PK assessments are detailed in the Schedule of Assessments (Appendix 1).

Note: patients will be randomized 2:1 (zetomipzomib 30 mg: placebo) 2:1 (zetomipzomib 60 mg: placebo) with N=83 Class III/IV +/-V patients per dose group (zetomipzomib 30 mg, zetomipzomib 60 mg, and placebo) and up to approximately N=10 pure Class V patients per treatment group. For the higher dose group, zetomipzomib or placebo will be administered at 60 mg following step up from an initial Week 1 dose of 30 mg. Patients will be stratified by: LN Class, average 24-hour UPCR at the Screening visit, and IV methylprednisolone planned total dose. IV=intravenous; LN=lupus nephritis; MMF=mycophenolate mofetil; MP=methylprednisolone; OCS=oral corticosteroid; po=oral; QD=once daily; QW=once weekly; SoC=standard of care; SC=subcutaneous; UPCR=urine protein to creatinine ratio.

Patients who permanently discontinue study treatment for any reason will be encouraged to remain in the study as outlined in the Schedule of Assessments (Appendix 1) through End of Study (EOS). If the patient cannot continue with the planned assessments, the Early Termination Visit (ETV) and the 4-week safety follow-up (EOS) visit will be accomplished at a minimum.

There will be an interim analysis (IA) when approximately 50% of the randomized patients with Class III/IV +/-V LN have completed or would have completed the Week 37 visit. This IA will serve the following purposes: (1) futility analysis and (2) a potential sample size increase up to 50% for patients with Class III/IV +/-V LN based on conditional power (CP).

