9.1.12. Exposure-Adjusted Incidence Rates

Exposure will be calculated within each treatment group as the total time at risk of the event across all patients. Exposure will be calculated differently depending on whether the subject did or did not experience the event in question. For patients who experienced the event, exposure is calculated as the number of days from the first dose of study treatment to the first occurrence of the event. For patients who did not experience the event, exposure is calculated as the number of days from first dose of study treatment to the end of study, inclusive. End of study is defined as the minimum of (treatment discontinuation date, treatment completion date, death date, lost to follow-up date).

The incidence rate (IR) for the given preferred term is calculated within treatment group as the number of patients (n) experiencing at least one occurrence of the event divided by the total time at risk for all patients in the treatment group. EAIR for the given preferred term will be computed as the number of events / 100 years of exposure. The difference (zetomipzomib – placebo) between EAIR along with a 95% CI for the difference will be reported separately for the zetomipzomib 30 mg and 60 mg dose groups using the normal approximation.

EAIR =
$$\frac{n}{T} = \frac{n}{\sum t_i}$$

The test statistic is given by (z=zetomipzomib, p=placebo):

$$E = \left(\frac{n_z}{T_z} - \frac{n_p}{T_p}\right) / \sqrt{\frac{n_z}{T_z^2} + \frac{n_p}{T_p^2}}$$

The 95% CI for the difference in EAIR will be calculated as follows:

$$\left(\frac{n_z}{T_z} - \frac{n_p}{T_P} \right) - Z_{\alpha/2} \sqrt{\frac{n_z}{T_z^2} + \frac{n_p}{T_p^2}} \ , \ \left(\frac{n_z}{T_z} - \frac{n_p}{T_P} \right) + Z_{\alpha/2} \sqrt{\frac{n_z}{T_z^2} + \frac{n_p}{T_p^2}}$$

Summary tables presenting the number and percentage of patients, exposure time, EAIR, and treatment comparisons will be provided for the following:

- TEAEs, overall and by SOC and PT
- TEAEs \geq Grade 3 by SOC and PT
- Serious TEAEs, overall and by SOC and PT
- TEAEs by severity grade with incidence of 5% and higher

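### AE collection has three written end points, and the exposure-adjusted incidence rate does not hold events and time at risk to one window

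*SAP*

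**What the plan says.** Three end points for AE collection are written:

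- Protocol 9.1.5: from consent, "continuing for 30 days following the last dose of zetomipzomib or placebo or the EOS visit, whichever occurs later". Protocol 9.2.2 sets the same limit for SAEs: "through 30 days after the last dose of zetomipzomib or placebo or the EOS visit, whichever occurs later".
- Footnote q of the Schedule of Assessments (Protocol Appendix 3, repeated in SAP Appendix 1): "starting at the time of informed consent and continuing through 4 weeks post-last dose". The row that this footnote annotates shows AE collection running through Weeks 53 and 56 and the early termination visit.
- SAP 9.1: "AEs from signing IC form through 30 days after last dose of study treatment will be recorded". There is no EOS alternative.

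The difference matters only for patients who stop drug and are still followed, which both documents encourage. Protocol 3.1: "patients who do not receive rescue therapy but undergo a permanent discontinuation of zetomipzomib or placebo will also be encouraged to remain in the study". SAP 3.1: "Patients who permanently discontinue study treatment for any reason will be encouraged to remain in the study". When EOS falls for such a patient is not settled. Protocol 7.1 and the schedule column label it Week 56, while footnote a says: "The end of study/safety follow-up visit will occur 4 weeks after the last dose of zetomipzomib or placebo".

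For the EAIR, SAP 9.1.12 gives a patient with the event the days from first dose to first occurrence, with no cut at end of treatment. An event-free patient contributes days to a date that the SAP calls end of study: "End of study is defined as the minimum of (treatment discontinuation date, treatment completion date, death date, lost to follow-up date". SAP 9.1 defines a TEAE as arising during treatment, or worsening against the pre-treatment state, and gives no last day on which an event can qualify.

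SAP Section 13 lists departures from the protocol as small as the addition of respiratory rate. It does not list the dropped EOS alternative.

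**The concern.** There are two linked problems.

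First, collection. A site working from footnote q, a site working from Protocol 9.1.5 and a programmer working from SAP 9.1 would each stop at a different date. For an early stopper who stays on study, the stretch in dispute is off-drug follow-up, sometimes on rescue treatment. AE incidence and severity is the primary safety endpoint, so which events belong in the database should not depend on which page was read.

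Second, the rate. An EAIR is interpretable when events and time at risk are taken from the same window. Here the numerator has no stated limit after treatment and the event-free denominator stops at treatment end. If a post-treatment event is accepted as a TEAE, it enters the numerator while the off-drug time of patients who had no event is left out. The rate is then too high, and more so in an arm with more discontinuation. SAP 9.1.12 puts a 95% CI on the zetomipzomib minus placebo difference, so an imbalance in discontinuation could appear as a difference in AE rate.

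**Working it through.** The documents give no AE rate, discontinuation rate or EAIR, so there is no stated figure to reproduce.

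**Step 1: dates.** Day of Week w = (w − 1) × 7 + 1.

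- Completer, last dose Week 52 = Day 358. Plus 28 days = Day 386, which is also Week 56. Plus 30 days = Day 388. The spread is 2 days.
- Last dose Week 13 = Day 85. Footnote q ends on Day 113 and SAP 9.1 on Day 115. Protocol 9.1.5 ends on Day 386 if EOS is Week 56. The gap is 386 − 115 = 271 days (38.7 weeks).
- Last dose Week 26: 386 − 206 = 180 days. Last dose Week 40: 386 − 304 = 82 days.
- If EOS is literally 4 weeks after last dose, the later of 28 and 30 days is 30 days. Protocol 9.1.5 then equals SAP 9.1 and the gap is 0.

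SAP Table 2 targets Day 393 for Week 56, which would add 7 days to each Week 56 gap.

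**Step 2: expected EAIR under SAP 9.1.12.** The assumptions are mine, not the documents': constant hazard h, the same in both arms and on or off drug; 10% of one arm and 30% of the other stop early; all stay to Week 56. Let T be end of treatment and W the last day on which an event is counted.

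- P(event) = 1 − exp(−hW)
- Expected days = [1 − exp(−hW)(1 + hW)]/h + exp(−hW) × T
- EAIR = 100 × sum of P(event) / (sum of days / 365.25)

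Worked case: h = 0.20/365.25 per day, all early stoppers leaving drug on Day 57, events counted to the later of last dose + 30 days and Day 386.

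- Early stopper (T = 57, W = 386): P = 0.1905, days = 81.62.
- Completer (T = 358, W = 388): P = 0.1914, days = 325.30.
- 10% stopping, per 100 patients: events = 10 × 0.1905 + 90 × 0.1914 = 19.13; PY = (10 × 81.62 + 90 × 325.30)/365.25 = 82.39; EAIR = 23.2.
- 30% stopping: events = 30 × 0.1905 + 70 × 0.1914 = 19.11; PY = (30 × 81.62 + 70 × 325.30)/365.25 = 69.05; EAIR = 27.7.

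The true rate is 20.0 in both arms. The same calculation with other event windows and stopping patterns gives:

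| Event window | Stopping pattern | 10% stop | 30% stop | False difference per 100 PY |
|---|---|---|---|---|
| To end of treatment | Either | 20.0 | 20.0 | 0 |
| Last dose + 30 days | Uniform, Weeks 1–52 | 21.6 | 21.8 | 0.2 |
| Last dose + 30 days | All Day 57 | 21.7 | 22.1 | 0.4 |
| Week 56 | Uniform, Weeks 1–52 | 22.5 | 24.8 | 2.3 |
| Week 56 | All Day 57 | 23.2 | 27.7 | 4.5 |

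For hazards of 5 to 100 per 100 PY and 10% to 40% uniform stopping, the rate within one arm is inflated by 5% to 10% (30-day window) or 7% to 34% (Week 56 window). With equal hazards and the same discontinuation pattern in both arms, the false difference is 0.

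**The case against.** The strongest defence is that the plan can be read coherently. EOS is tied to last dose by footnote a, so Protocol 9.1.5 and SAP 9.1 agree. A TEAE arises during treatment, so post-treatment events stay out of the numerator and the EAIR is a consistent on-treatment rate.

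The TEAE half stands as one admissible reading. The EOS half is weaker. With a visit window of ±2 days, an EOS fixed at 28 days after last dose could fall no later than day 30, so the later-of clause in Protocol 9.1.5 and 9.2.2 would have no effect. Patients who stop drug are also asked to follow the Schedule through EOS. Neither document says which meaning applies to them.

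Three stronger readings are tempting, and the documents do not support them:

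- A reader might infer that off-drug events are counted without their own person-time. They are not: SAP 9.1.12 runs an event patient's clock to the event, off-drug days included. The missing time belongs to event-free patients.
- A reader might infer that AEs in patients off drug will go unrecorded for most of follow-up. The schedule row still shows AE collection to Week 56, Protocol 9.2.2 separately covers SAEs, and sites collect under the protocol rather than the SAP. Footnote q contradicts its own row; it does not by itself end collection.
- A reader might infer that the primary safety comparison is biased. Cumulative incidence in SAP 9.1 uses no person-time, and Protocol 10.7 says only that exposure-adjusted rates may be provided. SAP 9.1.1, 9.1.4 and 9.1.11 also summarise or list all AEs, SAEs and deaths without a matching fatal TEAE, so later events recorded still reach an output.

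**Conclusion.** The concern holds in limited form. The three collection end points contradict each other and the change is undeclared. The practical gap is about 2 days for completers. It is months for early stoppers who stay on study only if EOS means Week 56 for them, and the documents leave that open.

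The EAIR rule is open to mismatch because the TEAE has no end day and event time is not cut where event-free time is. In the scenarios tested, any mismatch raises the rate, and raises it more with more discontinuation. The size rests on assumptions that the documents do not supply. At 20 per 100 PY with 30% against 10% discontinuation, the false difference is 0.2 to 0.4 per 100 PY with a 30-day event window and 2.3 to 4.5 with events counted to Week 56. The 4.5 needs every early stopper to leave drug at Day 57 and stay to Week 56, and should not be taken as the expected effect. A strictly on-treatment TEAE, or equal discontinuation under equal hazards, gives 0.

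**What to change.** 1. Bring Schedule footnote q (Protocol Appendix 3 and SAP Appendix 1) and SAP 9.1 into line with Protocol 9.1.5, and state what EOS means for a patient who stops drug and stays on study.
2. In SAP 9.1, give TEAE an explicit end day, for example last dose + 30 days, and list later events separately as post-treatment.
3. In SAP 9.1.12, apply that same limit to the events counted and to event-free time at risk, which would end at the earliest of that limit, death, loss to follow-up or study exit. A strictly on-treatment window would also be coherent, provided that it governs both.
4. Record the change in SAP Section 13, before unblinding.

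The cost is wording only. AE recording uses visits already scheduled. With a 30-day limit applied on both sides, reported rates would be slightly lower than under the present denominator with the same events.
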